|  | 
[REDACTED]
 
The duration of the DPC period for each patient will be 36 weeks. The octreotide capsule dose/placebo should be titrated up per Investigator's discretion, based on significantly increased IGF-1 levels compared to Baseline (average of the 2 assessments within 2 weeks prior to randomization), worsening of acromegaly signs/symptoms or both.
 
The Sponsor recommends any one of the following guiding rules for dose escalation:
 
 
• Significantly increased IGF-1 levels compared to Baseline defined as IGF-1 increase by at least 30% to <math>>1 \times \text{ULN}</math> (this will be flagged by the central laboratory).
 
• IGF-1 levels <math>>1 \times \text{ULN}</math> for 2 consecutive visits.
 
• New or worsening of any one of the following acromegaly signs/symptoms: headache, fatigue, perspiration, soft tissue swelling, arthralgia, dysglycemia or hypertension or other signs that in view of the Investigator are related to acromegaly.
 
 
The dose escalation will be done in a stepwise manner from 1 capsule twice daily; BID (equivalent to 40 mg/day) to 2 capsules in the morning and 1 capsule in the evening/night (equivalent to 60 mg/day) to 2 capsules BID (equivalent to 80 mg/day).
 
The dose can be escalated any time through Week 24 (including Week 24); thereafter the dose must be kept stable. Patients randomized to matching placebo will also undergo mock titrations increasing capsule numbers from 1 capsule twice daily to 2 capsules in the morning and 1 capsule in the evening/night to 2 capsules BID.
 
During the DPC period, patients will return to the clinic for a site visit every four weeks up to week 36 (<math>\pm 5</math> days) and attend an additional in-clinic visit at week 34 (<math>\pm 5</math> days).
 
[REDACTED] Pre-scheduled telephone calls will occur at Weeks 1 and 2. Unscheduled visits will be allowed throughout the study for safety, tolerability or management of active disease, per the Investigator discretion.
 
[REDACTED]
 
All efforts should be made to maintain patients on their randomized arm assignment throughout the DPC period up to completion of the core study.
 
Patients who meet the pre-defined withdrawal criteria [(IGF-1 levels <math>\geq 1.3 \times \text{ULN}</math> AND exacerbation of acromegaly clinical signs or symptoms), for 2 consecutive
 |
|--|---|

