### 5.2.3 DPC Clinic Visits (Weeks 4, 8, 12, 16, 20, 24, 28, 32, 34, 36)

The following procedures and assessments will be conducted during DPC period visits:

- Weight
- Vital signs
- Safety laboratory tests: hematology and biochemistry
- IGF-1
- Acromegaly directed and treatment directed physical examination
- AEs including GI
- Concomitant medications recording
- Assess pre-define withdrawal criteria (based on clinical judgement, consider the option for an unscheduled visit in case IGF-1 levels  $\geq 1.3 \times \text{ULN}$  while treated for at least 2 weeks with 4 capsules a day and/or patient reports significant exacerbation of acromegaly symptoms)
- Assessment of dose titration (through week 24)
- Dispense study medication (call IVRS/IWRS)
- Drug administration instructions
- Study medication accountability
- Compliance assessment (with drug administration instructions)

***When results of IGF-1 are available from this visit assess whether additional unscheduled visits are required to confirm active disease.*** For a patient with a single visit IGF-1 level  $\geq 1.3 \times \text{ULN}$  a second sample will be obtained within 2 weeks of the first assessment. for a total of 2 consecutive IGF-1 assessments for confirmation of disease activity. Patients who miss week 34 visit, or have missing IGF-1 level from week 34 visit, will be scheduled to attend an unscheduled visit to collect blood draw for IGF-1 levels.

In addition to the above assessments, the following assessments will be done at Week 36:

- Laboratory tests: urinalysis, TSH, free T4, and lipid profile (total cholesterol, triglycerides, high-density lipoprotein, and low-density lipoprotein) and HbA1c; serum pregnancy test in women of childbearing potential
- GH
- Physical examination
- ECG
- Gall bladder ultrasound
- Treatment Period completion form

Patients who meet the pre-defined withdrawal criteria, IGF-1  $\geq 1.3 \times \text{ULN}$  AND exacerbation of

---

 GH: Five samples collected every  $30 \pm 5$  minutes over two hours, 2-4 hours after study medication administration in the clinic, (patients to fast 4 hours prior to and the 2 hours during GH sampling)

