## 3 Study Design

This will be a phase 3, randomized, double-blind, placebo-controlled, multicenter study to evaluate the safety and efficacy of octreotide capsules in acromegaly patients who previously tolerated and demonstrated biochemical control on injectable SRL treatment.

Patients meeting the pre-defined withdrawal criteria, IGF-1  $\geq 1.3 \times \text{ULN}$  AND exacerbation of acromegaly clinical signs or symptoms compared to baseline, for 2 consecutive assessments, while treated for at least two weeks with 4 capsules per day, during the DPC period, will be rescued with injectable SRL treatment used prior to Screening and will continue to be followed per protocol until week 36. At week 36, these patients will be offered to enter the OLE period and receive octreotide capsules. Patients who do not complete the full 36-week DPC period will not be eligible to enter the OLE period and will not require further follow up beyond week 36.

Patients who discontinue study medication early during the DPC period for reasons other than the pre-defined withdrawal criteria, should continue to be followed per protocol until week 36. The Sponsor recommends re-initiation of their prior injectable SRL treatment (as rescue or escape medication) upon meeting the pre-defined withdrawal criteria described above. These patients will not be eligible to enter the OLE period and will not require further follow up beyond week 36.

Patients who discontinue study medication during the OLE period, for any reason, or have completed the 36-week DPC period on study medication and are ineligible or not opting to continue into the OLE period, will revert to their prior injectable SRL treatment (prior to Screening) or other treatment as determined by their physician. These patients will be followed-up for 12 weeks after end of treatment (EOT).

Database lock for the DPC period will occur after the last patient completes the DPC period. At this timepoint, the study will be unblinded and all data from the DPC period analysed. Interim analyses of the OLE period will be conducted periodically, after completion of the DPC period. Data collected post DPC period (week 36) in patients not entering the OLE period and those who entered the OLE period will be included in the OLE database.

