### **6.9.3 Laboratory Parameters**

Descriptive summary statistics for chemistry and hematology data at each post randomization time point (both absolute and change) will be presented by final dose group and treatment group (i.e., octreotide 40, 60, 80, overall and placebo). Summaries will be provided for the DPC period and for the OLE period. In calculating the change from baseline for both the DPC and for the OLE, the baseline for the DPC period will be used.

Shift tables, summarizing individual subject changes from baseline to end of treatment will be presented for each laboratory parameter, by treatment group, using the normal ranges from the central laboratory. An additional shift analysis will be presented for glucose using the levels within the common terminology criteria for adverse events (CTCAE) version 4.03. Summaries will be provided for both the DPC period and OLE period. For both the DPC period and the OLE period summaries, baseline will be the baseline defined for the start of the DPC period.

Subjects with clinically significant abnormalities (based on investigator’s assessment) will be identified in listings.

All tabular summaries will exclude any data that was collected after a subject had discontinued study drug. Data collected after a subject had discontinued study drug will be included in listings.

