### 6.9.5 ECG

All 12-Lead ECGs will be read by a central lab. 12-Lead ECG parameters will be summarized at each time point using descriptive statistics by final dose group and treatment group (i.e., octreotide 40, 60, 80, overall and placebo). Both absolute and change from baseline will be provided for each continuous 12-Lead ECG parameter. Summaries will be provided for the DPC period and for the OLE period. In calculating the change from baseline for both the DPC and for the OLE, the baseline for the DPC period will be used.

Additionally, the numbers and percentages of patients with ECG abnormalities (as determined by the central laboratory) at each visit will be presented for both the DPC and for the OLE. The parameters and abnormality criteria are specified in the table below:

Parameter	Abnormality Criterion
PR interval	<110 ms
	>300 ms
QRS interval	$\geq$ 120 ms
QTcF	<350 ms
	Male >450 ms or Female >470 ms
	>500 ms
Heart rate	<50 bpm
	>110 bpm

Shift tables will be used to show the changes from baseline to each post baseline time point based on the above abnormality criteria for both the DPC and for the OLE periods. For both the DPC period and the OLE period, shifts from baseline will use the baseline defined for the start of the DPC period.

A listing of patients with clinically significant ECG abnormalities (using the high and low cut points above) will be provided in listings.

All tabular summaries will exclude any data that was collected after a subject had discontinued study drug. Data collected after a subject had discontinued study drug will be included in listings.

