### 6.9.6 Abdominal Ultrasound

The following information will be summarized at baseline and end of treatment for the DPC period using shift tables, by final dose group and treatment group (i.e., octreotide 40, 60, 80, overall and placebo):

- Ultrasound Normality (Normal=Yes reported on eCRF; Abnormal = No)
- Biliary Sludge (Normal=No reported on eCRF; Abnormal =Yes)
- Wall Thickening (Normal=No reported on eCRF; Abnormal =Yes)
- Dilatation of Common Bile Duct (Normal=No reported on eCRF; Abnormal =Yes)

For the OLE period, shift tables will also be provided to show shifts from baseline of the DPC period to each assessment in the OLE period.

All tabular summaries will exclude any data that was collected after a subject had discontinued study drug. Data collected after a subject had discontinued study drug will be included in listings.

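### OLE safety change and shift tables use only the DPC baseline, so for ex-placebo and rescued patients they do not separate change on open-label capsules from change already present at Week 36

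*SAP*

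**What the plan says.** SAP 6.9.3 (laboratory) sets one reference for both periods: "In calculating the change from baseline for both the DPC and for the OLE, the baseline for the DPC period will be used". For the shift tables it adds: "For both the DPC period and the OLE period summaries, baseline will be the baseline defined for the start of the DPC period". SAP 6.9.4 (vital signs and weight) has the same rule. So does SAP 6.9.5 (ECG), where "shifts from baseline will use the baseline defined for the start of the DPC period". SAP 6.9.6 (ultrasound) plans OLE tables "to show shifts from baseline of the DPC period to each assessment in the OLE period". Protocol 8.4.8.2 to 8.4.8.4 agrees with the SAP throughout. No visible section adds a change from OLE entry for any of these parameters. SAP 6.5 does define a baseline of the OLE, but only for IGF-1 and GH as descriptive characteristics.

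On the treatment received before the OLE, the protocol synopsis states: "The duration of the DPC period for each patient will be 36 weeks". SAP section 3 says that patients who meet the withdrawal criteria "will be rescued with injectable SRL treatment used prior to Screening and will continue to be followed per protocol until week 36", after which they may enter the OLE. SAP 6.9 groups the OLE summaries by treatment group according to DPC arm. SAP 6.9.3 to 6.9.6 each keep data collected after stopping study drug out of the tables and show them in listings only.

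**The concern.** The OLE objective is the long-term efficacy and safety of octreotide capsules. For an octreotide-arm patient who was not rescued, the DPC baseline is the last state before the first capsule, so it suits that objective. For two other groups it does not isolate the capsules:

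- **Ex-placebo patients** were on injected SRL at DPC baseline, then had placebo (followed by injected rescue in some), and took their first octreotide capsule at OLE entry.
- **Rescued patients of either arm** were on injected SRL between stopping study drug and Week 36.

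In both groups the OLE tables combine change that arose before the first open-label capsule with change after it. The parameters matter: the protocol lists dysglycemia and hypertension among the signs of exacerbation (5.2.3, 7.1.1), and the SAP plans CTCAE shift tables for glucose and blood pressure (6.9.3, 6.9.4). What is at stake is how the OLE safety tables are read for newly exposed patients. No test is involved.

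**Working it through.** **1. The rule by domain.**

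| Domain | SAP | Protocol | OLE reference | Display from OLE entry |
|---|---|---|---|---|
| Laboratory | 6.9.3 | 8.4.8.2 | DPC baseline | none |
| Vital signs, weight | 6.9.4 | 8.4.8.3 | DPC baseline | none |
| ECG | 6.9.5 | 8.4.8.4 | DPC baseline | none |
| Ultrasound | 6.9.6 | 8.4.8.4 | DPC baseline | none |

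**2. The identity.** For any patient and parameter:

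reported OLE change = OLE value − DPC baseline = (Week 36 − DPC baseline) + (OLE value − Week 36).

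The second term is the change on open-label capsules. The first term enters in full. In arbitrary units:

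| Change by Week 36 | Change in OLE | Reported from DPC baseline | Reported from OLE entry |
|---|---|---|---|
| +10 | 0 | 10 + 0 = +10 | 0 |
| +10 | −10 | 10 − 10 = 0 | −10 |
| 0 | +10 | 0 + 10 = +10 | +10 |

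The first row shows an OLE change when nothing happened on open-label capsules. The second hides a real change. The third shows that the two references agree when nothing had changed by Week 36.

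**3. Who is affected.**

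| Patient | Treatment from DPC baseline to Week 36 | Week 36 state visible in DPC tables? |
|---|---|---|
| Octreotide, not rescued | capsules | yes |
| Octreotide, rescued | capsules, then injected SRL | no, tables stop when study drug stops |
| Placebo, not rescued | placebo | yes |
| Placebo, rescued | placebo, then injected SRL | no, tables stop when study drug stops |

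For the second and fourth rows, the net change at Week 36 is first tabulated as part of an OLE change.

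**4. Illustration for shift tables.** About 50 patients randomized 1:1 (SAP 3.1, 3.2) give 50 × 1/2 = 25 on placebo. That is an upper bound for ex-placebo OLE patients, reached only if all of them enter. Suppose a share q becomes abnormal by Week 36, a share r of those stays abnormal, and capsules have no effect. The expected shifts from DPC baseline are then 25 × q × r. The documents give neither q nor r, so both are assumptions.

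| q | r = 1 | r = 0.5 |
|---|---|---|
| 5% | 1.25 | 0.6 |
| 10% | 2.5 | 1.25 |
| 20% | 5.0 | 2.5 |
| 30% | 7.5 | 3.75 |

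Measured from OLE entry, each cell shows 0 new shifts.

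**5. The OLE-entry value exists.** Appendix A, footnote 2, makes DPC Week 36 the first OLE visit. Protocol 5.2.3 schedules weight, vital signs, hematology and biochemistry at every DPC clinic visit. It then says "In addition to the above assessments, the following assessments will be done at Week 36" and lists, among others, lipids, HbA1c, ECG and gall bladder ultrasound.

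**The case against.** The strongest reply is that this is a choice between valid references, made explicitly and identically in protocol and SAP. All patients were on stable injected SRL at DPC baseline. Change from that point compares long-term capsule use with previous established therapy, which is a fair question in a switch population. For unrescued ex-placebo patients, Week 36 follows 36 weeks of placebo; if values worsened in that time, using it as the only reference could flatter the capsules. This stands, and it argues against replacing the DPC baseline.

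Much else in the plan separates the periods, and this also stands:

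- Absolute values are shown for laboratory tests, vital signs and ECG, and ECG abnormalities are counted by visit.
- OLE adverse events are dated from the end of DPC treatment (SAP 6.9.2.2), so the baseline rule does not touch them. For a rescued patient that date is the last blinded dose, but this is a separate dating matter.
- Grouping by DPC arm keeps ex-placebo patients visible, and the DPC tables show the placebo arm's own changes.

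These safeguards are incomplete. The ex-placebo column still adds the two terms together, and summaries that combine the arms mix baselines with different meanings. Group summaries of absolute values do not give within-patient shifts. For rescued patients the DPC tables stop too early to help.

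A Week 36 reference has weaknesses of its own. Blood at that visit needs only a 4-hour fast (Protocol 5.8.7), while CTCAE hyperglycaemia grades 1 and 2 are defined on fasting glucose (Protocol Table 3). Rescued and unrescued placebo patients are in different treatment states at Week 36, so they should not be pooled. A rescued patient's Week 36 value also falls under the exclusion of data collected after stopping study drug. Finally, ECG is not among the routine OLE procedures (Protocol 5.3, Appendix A), so few OLE ECG tables are concerned.

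**Conclusion.** The point holds as a gap in presentation. For ex-placebo patients, and for rescued patients of either arm, the planned OLE change and shift tables carry forward any net change present at Week 36 that persists, and they hide one that reverses on capsules. This follows from the identity alone and needs no assumption about rates.

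A reader might go further in three ways that the documents do not support:

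- *Everything that changed on placebo is reported as a capsule effect.* Only a net change still present at the OLE assessment is carried over, and only into change and shift tables.
- *The DPC baseline is wrong and the OLE safety objective cannot be answered.* Change from study entry is a valid long-term summary, and the plan has other displays that partly separate the periods.
- *The placebo arm can be relied on to deteriorate, so the distortion is large.* The primary hypothesis says only that more patients keep control on octreotide, and Protocol 5.3 provides for patients who keep their response on placebo.

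The upper bound is about 25 ex-placebo patients, plus rescued octreotide-arm patients whose number the documents do not give. The size of the effect cannot be taken from the documents; the counts in the working rest on assumed rates. Safety analyses are descriptive (SAP 6.9), so no error rate, power or DPC conclusion changes. This is a worthwhile, inexpensive improvement.

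**What to change.** In SAP 6.9.3 to 6.9.6, with matching text in protocol 8.4.8.2 to 8.4.8.4:

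1. Keep all tables against the DPC baseline as planned.
2. Add, for the OLE set, change and shift tables from the Week 36/OLE-entry value, defined as the last value before the first open-label capsule. Show them by DPC arm and by rescue status.
3. Give priority to laboratory tests, vital signs with weight, and ultrasound. ECG can come last, since it is not a routine OLE procedure.
4. State that the exclusion of data collected after stopping study drug does not remove a rescued patient's Week 36 value as the OLE-entry reference, or that patient's OLE data. Read literally, it could remove both, although SAP 6.9 says that OLE safety analyses include data collected in the OLE.
5. Footnote that Week 36 glucose and lipids follow only a 4-hour fast. They are best compared with OLE visits under the same condition: Months 6 and 12, every 12 months after that, and the last OLE visit (Appendix A, footnote 9).

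The cost is SAP and protocol wording, one more baseline flag and an additional set of tables. No new data are needed. The remaining drawback is that glucose and lipid changes from Week 36 to OLE visits with an overnight fast need cautious reading.

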### **Liver Dysfunction**

Somatostatin analogs including octreotide have been associated with liver function abnormalities, as well as sporadic post-marketing reports of acute hepatitis with or without cholestasis, jaundice and cholestatic jaundice.

Octreotide inhibits secretion of cholecystokinin, resulting in reduced contractility of the gallbladder and an increased risk of sludge and stone formation. Biliary disease is the most common reasons for liver dysfunction in acromegaly patients.

Liver function tests (ALT, AST and Bilirubin), will be monitored routinely at all scheduled visits during all periods of the study. Liver function tests could also be assessed at any unscheduled study visit, as clinically indicated.

Patients who develop liver function abnormalities (elevated transaminases to  $>3 \times \text{ULN}$ ) during the study should be evaluated for common causes of hepatitis such as cholestasis, alcoholic liver disease, non-alcoholic steatohepatitis, environmental exposures, other drug/herbal supplement exposures, viral or autoimmune hepatitis. The diagnostic work up of liver dysfunction should be guided by the patient's medical history and physical exam, and local practice, at the investigator discretion.

Patients with asymptomatic liver dysfunction (i.e., ALT or AST  $>3 \times \text{ULN}$  and  $< 5 \times \text{ULN}$  and total bilirubin  $< 2 \times \text{ULN}$ ), may continue to receive study drug (Figure 2). Liver function tests must be repeated in 7 days. In case of continued transaminase elevation, periodical follow up visits should be considered, per the investigator discretion up to resolution/return to baseline. Follow up should include monitoring of symptoms potentially associated with acute hepatitis (new appearance of fatigue, nausea, vomiting, right upper quadrant pain or tenderness, fever, rash, and/or eosinophilia), or with complications of cholestasis (e.g. cholangitis). In case of symptoms suggestive of cholestasis, a follow up abdominal ultrasound should be considered. Local assessment of INR could be added to the liver function tests, based on the investigator discretion.

[figure not shown]

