All patients who develop significant liver dysfunction (ALT or AST  $\geq 5 \times \text{ULN}$ ) should have study drug held and be followed up within 3 days and every 3-4 days thereafter up to resolution/return to baseline. In case ALT/AST remains above  $5 \times \text{ULN}$ , study drug should be discontinued. If ALT/AST has fallen to  $>3 \times \text{ULN}$  and  $< 5 \times \text{ULN}$ , patients should be managed as described in the previous paragraph.

If liver function tests normalize or return to baseline, while study drug has been held, the decision to resume study drug must be discussed with the study medical monitor.

If no alternative etiology exists study drug should be discontinued in the following scenarios:

- ALT or AST  $>5 \times \text{ULN}$  for at least 2 weeks
- ALT or AST  $>3 \times \text{ULN}$  and (TBL  $>2 \times \text{ULN}$  or INR  $>1.5 \times \text{ULN}$ )
- ALT or AST  $>3 \times \text{ULN}$  with new appearance of fatigue, nausea, vomiting, right upper quadrant pain or tenderness, fever, rash, and/or eosinophilia ( $>5\%$ ).

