#### **8.4.8.2 Laboratory Assessments**

Descriptive summary statistics for chemistry and hematology data at each post randomization time point (both absolute and change) will be presented by final dose group and treatment group (i.e., octreotide 40, 60, 80, overall and placebo). Summaries will be provided for the DPC period and for the OLE period. In calculating the change from baseline for both the DPC and for the OLE, the baseline for the DPC period will be used.

Shift tables, summarizing individual subject changes from baseline to end of treatment will be presented for each laboratory parameter, by treatment group, using the normal ranges from the central laboratory. Summaries will be provided for both the DPC period and OLE period. For both the DPC period and the OLE period summaries, baseline will be the baseline defined for the

start of the DPC period.

Subjects with clinically significant abnormalities (based on investigator's assessment) will be identified in listings

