## 6.2 Visit Windows

The following table outlines the analysis visits that data will be mapped to for analysis of data collected during Screening and the DPC period. Data will be analysed using the nominal visit, except in the case of an unscheduled visit that occurs between week 34 and week 36 which is in the place of a missing week 34 visit. These visits will be mapped to the scheduled visit (i.e., week 34). All other unscheduled visits will be listed, but not mapped to a specific analysis visit.

Study Visit	Analysis Visit
Screening 1	Screening 1
Screening 2	Screening 2
Baseline	Baseline
Week 4	Week 4
Week 8	Week 8
Week 12	Week 12
Week 16	Week 16
Week 20	Week 20
Week 24	Week 24
Week 28	Week 28
Week 32	Week 32
Week 34	Week 34
Week 36	Week 36

The following table outlines the analysis visits data will be mapped to for analysis of data collected during the OLE period. Data will be analysed using the nominal visit. All unscheduled visits will be listed, and included in derivations, but not mapped to a specific analysis visit.

Study Visit	Analysis Visit
Baseline	Baseline
Week 4	Week 4
Week 8	Week 8
Week 12	Week 12
Week 16	Week 16
Week 20	Week 20
Week 24	Week 24
Week 36	Week 36
Week 46	Week 46
Week 48	Week 48
Week 60, 72, 84, ... (i.e, every 12 weeks)	Week 60, 72, 84, ... (i.e, every 12 weeks)

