### **6.9.4 Vital Signs and Body Weight**

Descriptive statistics of vital sign (systolic blood pressure, diastolic blood pressure, heart rate, body weight) data at each post randomization time point (both absolute and change) will be presented by final dose group and treatment group (i.e., octreotide 40, 60, 80, overall and placebo). Summaries will be provided for the DPC period and for the OLE period. In calculating the change from baseline for both the DPC and for the OLE, the baseline for the DPC period will be used.

Additionally, shift tables, summarizing individual subject changes from baseline to end of treatment will be presented for heart rate, diastolic and systolic blood pressure, by final dose group and treatment group (i.e., octreotide 40, 60, 80, overall and placebo), using the categories outlined in the common terminology criteria for adverse events (CTCAE) version 4.03.

These will be presented for both the DPC period and OLE period. For both the DPC period and the OLE period, shifts from baseline will use the baseline defined for the start of the DPC period.

Subjects with clinically significant abnormalities will be identified in listings.

All tabular summaries will exclude any data that was collected after a subject had discontinued study drug. Data collected after a subject had discontinued study drug will be included in listings.

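### Laboratory shifts run only from baseline to end of treatment in normal-range categories, so no table counts patients per arm by their peak ALT, AST or bilirubin in multiples of ULN

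*SAP*

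**What the plan says.** **Laboratory shifts.** SAP 6.9.3: "Shift tables, summarizing individual subject changes from baseline to end of treatment will be presented for each laboratory parameter, by treatment group", using the central laboratory's normal ranges. Protocol 8.4.8.2 has the same two-point design: "Shift tables, summarizing individual subject changes from baseline to end of treatment will be presented for each laboratory parameter". Data collected after a patient has discontinued study drug are left out of the tables and only listed. Glucose gets an extra shift in CTCAE levels; liver tests do not.

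**Other shifts in the same SAP.** For vital signs (SAP 6.9.4), "shift tables, summarizing individual subject changes from baseline to end of treatment will be presented for heart rate, diastolic and systolic blood pressure", in CTCAE categories. For ECG (SAP 6.9.5), the design is different: "Shift tables will be used to show the changes from baseline to each post baseline time point based on the above abnormality criteria".

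**Liver monitoring.** Protocol 7.6 says that liver tests "will be monitored routinely at all scheduled visits during all periods of the study". Asymptomatic ALT or AST between 3 and 5 × ULN with bilirubin below 2 × ULN may continue on drug, with a repeat test after 7 days. Patients with ALT or AST at or above 5 × ULN "should have study drug held and be followed up within 3 days and every 3-4 days thereafter up to resolution/return to baseline". If the tests return to normal or to baseline "while study drug has been held, the decision to resume study drug must be discussed with the study medical monitor".

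**Unscheduled visits.** SAP 6.2 maps an unscheduled DPC visit only when it replaces a missed Week 34 visit. Otherwise: "All other unscheduled visits will be listed, but not mapped to a specific analysis visit".

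**The concern.** The protocol names liver dysfunction as a risk of the drug class and acts on specific multiples of ULN. The planned shift table loses information about those multiples in two ways. It uses one post-baseline value, so a rise that has resolved leaves no trace in it. It also uses normal-range categories, so 1.1 × ULN and 10 × ULN fall in the same cell. A reader of the study report could not see from any table how many patients in each arm passed 3 × or 5 × ULN, or had raised transaminases and raised bilirubin together. With about 25 patients per arm, a single such patient matters to the description of safety.

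**Working it through.** **1. How many scheduled values reach the shift table.** Protocol 5.2.3 lists DPC clinic visits at Weeks 4, 8, 12, 16, 20, 24, 28, 32, 34 and 36, each with biochemistry, so there are 10. SAP 6.9.3 does not define end of treatment for laboratory values; taking it as Week 36 for a patient who completes on drug, 1 visit is used and 10 − 1 = 9 are not.

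**2. What each course looks like in the planned outputs.**

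| Course on treatment | Shift table cell | Elsewhere |
|---|---|---|
| Normal baseline, asymptomatic rise to 3–5 × ULN, no dose change, resolved | Normal to Normal | By-visit maximum if drawn at a scheduled visit; an AE only if it meets another criterion in Protocol 7.1, such as the investigator's view of clinical significance |
| Normal baseline, rise to ≥ 5 × ULN, drug held, resolved, drug resumed | Normal to Normal | As above, and an AE, because the dosing schedule changed |
| Normal baseline, rise to ≥ 5 × ULN, drug held and not resumed | Depends on which value counts as end of treatment; if it is the spike, Normal to High | As above, and an AE |
| Baseline 1.5 × ULN (exclusion 15 bars only values above 3 × ULN), last value 10 × ULN | High to High | By-visit maximum if at a scheduled visit |

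No row leads to a count of patients by multiple of ULN.

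**3. Illustration.** These inputs are assumptions, not taken from the documents: 25 patients in an arm, all with ALT 0.6 × ULN at baseline; one peaks at Week 12, returns to 0.6, resumes drug and completes. The Week 12 mean is (24 × 0.6 + peak) / 25.

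| Peak (× ULN) | Normal-to-High, end of treatment | Normal-to-High, worst on-treatment | Week 12 mean | Week 12 median | Week 12 maximum |
|---|---|---|---|---|---|
| 3.5 | 0/25 | 1/25 | 0.716 | 0.6 | 3.5 |
| 5 | 0/25 | 1/25 | 0.776 | 0.6 | 5 |
| 6 | 0/25 | 1/25 | 0.816 | 0.6 | 6 |
| 10 | 0/25 | 1/25 | 0.976 | 0.6 | 10 |

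The end-of-treatment shift misses the patient at every peak, and the by-visit maximum finds the value. The worst-value shift finds the patient, but in normal-range categories it gives the same 1/25 for 3.5 and for 10 × ULN. Both changes are needed: the worst value and the ULN bands.

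**4. What the remaining outputs add.**

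- *By-visit summaries.* SAP 6.1 includes the maximum. It shows how high the highest value at a visit was, not how many patients passed a threshold, and it cannot link ALT and bilirubin in one patient. The rechecks after 7 days or every 3–4 days fall mostly between the scheduled visits; under SAP 6.2 a peak found there is only listed.
- *AE tables.* Intensity follows Protocol Table 1, which grades by symptoms and interference with daily life. A large asymptomatic rise can be tabulated as mild.
- *Listings.* Laboratory abnormalities are flagged there on the investigator's judgement of clinical significance, without counts by arm.

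**The case against.** The strongest reply is that the safety report does not lose these patients. A rise that leads to a hold meets the AE definition in Protocol 7.1 and is tabulated by arm at worst intensity. A spike at a scheduled visit appears as a by-visit maximum, abnormal cases are listed, and the IDMC reviews safety data. The thresholds in Protocol 7.6 are triggers for managing patients, and nothing in the documents makes them analysis categories. The safety analysis is descriptive throughout.

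Most of this stands, and it rules out three stronger readings that a reader might infer.

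- *That the report as a whole understates toxicity.* The documents do not support this, because the other outputs can show the event. The gap is in counting by size.
- *That Protocol 7.6 sends every held patient back on drug and so to a normal final value.* It directs a hold and follow-up; resumption depends on a discussion with the medical monitor. If drug is stopped for good, later values drop out of the tables, and the spike may be the value tabulated.
- *That blood pressure has the same gap.* Its shift is also two-point, but hypertension is an AESI graded by CTCAE (Protocol 7.1.1, Table 4), and SAP 6.9.2.1 summarises each AESI at worst intensity. Liver tests are not on the named AESI list.

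What the reply does not answer is the asymptomatic 3–5 × ULN rise with no dose change, which need not be an AE, and the peak seen only at an unscheduled recheck. Neither enters any count by arm.

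**Conclusion.** The point holds as a gap in safety reporting. For ALT, AST and bilirubin, the visible plan has no table that counts patients per arm by worst on-treatment value in multiples of ULN, and the planned shift table cannot supply one. The conclusion rests on the text of SAP 6.2, 6.9.3 and Protocol 7.6 and on no redacted figure.

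In scale, one uncounted patient is 1/25 = 4% of an arm, taking about 50 patients randomised 1:1. That is the weight of a single case, not an expected loss: the documents give neither the frequency nor the duration of such elevations in this trial. The primary and secondary efficacy analyses are unaffected. It is worth correcting because it is cheap and because the SAP already uses numeric cut-points at each time point for ECG and graded levels for glucose.

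**What to change.** In SAP 6.9.3, add by treatment group:

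1. A shift from baseline to worst (highest) on-treatment value for ALT, AST and total bilirubin, using the limits already in Protocol 7.6 as reporting bands: ALT and AST above 3 × and at or above 5 × ULN, bilirubin above 2 × ULN.
2. A count of patients with ALT or AST above 3 × ULN together with bilirubin above 2 × ULN.
3. A statement that unscheduled values and values drawn during a temporary hold are included, up to permanent discontinuation, with the date that marks discontinuation when a hold is never lifted. SAP 6.2 needs a matching exception for the DPC period.
4. A definition of end of treatment for laboratory values.

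Keep the end-of-treatment shift. A worst-category shift for blood pressure and heart rate is optional; if added, it must say which direction is worst.

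The cost is one or two tables from data already collected, and a laboratory picture that may look somewhat less favourable. No clinical rule changes.
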